1.3 SCHEDULE OF ACTIVITIES (SOA)

Study Procedures	≤30 weeks + 6 days thru 36 weeks + 6 days	32 weeks + 0 days thru 36 weeks + 6 days	Target: 1 day post last routine caffeine dose (but window of up to 3 calendar days allowed)	1 week on study drug (up to 14 days post 1 st dose)	36 weeks + 0 days PMA	Hospital Discharge	40 weeks + 0 days PMA	42 weeks + 6 days PMA	43 weeks + 6 Days PMA
Screening	X								
Informed Consent		X							
Enrollment		X							
Baseline Data Collection		X							
Pulse oximetry recording						X ¹⁰			
Randomization			X						
Once daily study drug				X ¹					
Twice daily study drug							X ¹		
Drug log						X			
Saliva for caffeine level				X			X ²		
Biomarker blood sample		X ³				X ³			
MRI/MRS		X ⁴							X ⁴
Pre-discharge checklist						X ⁵			
Weekly parent phone contact							X ⁶		
Infant sleep Q								X ⁷	
End of study visit									X ⁸
Concomitant medications					X ⁹				
Adverse Event					X ⁹				

1. Study drug (caffeine base 5 mg/kg QD or placebo, weight adjusted weekly while in hospital) begins 1 day after last day of routine caffeine, but no later than the 3rd calendar day after last dose of routine caffeine. Dose is increased to 5 mg/kg BID at 36 + 0; finally, the last dose of study drug is at 42 + 6. Note that initial dose will be BID if enrolled at 36 + 0 or later.
2. 2nd caffeine level targeted at 40 + 0, (no earlier than 39 + 0 and no later than last day of study drug), whether in hospital or at home.
3. 1st biomarker blood sample should be obtained as close as possible to the day of randomization. Whenever possible, this blood sample should be timed with a clinically required blood draw. To facilitate obtaining this sample at the time of a clinical blood draw, this sample may be obtained at any time after consent, but no later than the 2nd calendar day after the first dose of study drug. The 2nd sample is to be obtained at 38 + 0 (+ or - 3 days) or within 2 calendar days prior to hospital discharge, whichever comes first.
4. 1st MRI/MRS is done in hospital sometime between enrollment and 3 calendar days after starting study drug. 2nd MRI/MRS is targeted at 43 + 0 but should be no later than 46 + 6. MRI visit may be combined with the end of study visit. MRI/MRS scans will only be performed for subjects enrolled at sites participating in the MRI/MRS portion of the study.

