5. Includes documentation of tracking information, and parent training including: use of oximeter, drug administration, use of drug administration log, salivary sample collection, communication expectations and follow-up plans.
6. Weekly phone calls from study staff to parent(s) begin 1- 3 days after hospital discharge and continue through end of study follow up visit. A phone follow-up form will be completed to collect clinical data, adverse events, and document family questions.
7. Sleep Assessment (BISQ) done over the phone with parent at 42 weeks.
8. The end of study visit, which may be done remotely, is targeted for 43 + 6 days, or one week after the last dose of study drug, whichever comes first, but should be completed no later than 46 + 6. Study staff will collect the study drug log, used bottles, unused drug, study oximeter, and frozen salivary sample. Items may be shipped back if the parents opt for a remote visit.
9. Collection of concomitant medications and adverse event monitoring and reporting are continuous throughout study.
10. Home-oximetry will only be performed for subjects enrolled at sites participating in the home-oximetry portion of the study.

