6.5.1 RESCUE MEDICINE

As noted above, rescue therapy with open-label caffeine therapy is discouraged. Recurrent apnea-related symptoms have not occurred in preliminary studies after stopping routine caffeine.^{18,90} However, in the event that an infant has apnea-related clinical symptoms after stopping routine caffeine and starting study drug, study drug should be continued, and if judged to be needed by the clinical team, nasal CPAP or nasal cannula is the preferred additional therapy. If the clinical team ultimately decides that open-label caffeine must be used, we suggest the following: 1) Hold study drug; 2) begin open-label maintenance caffeine citrate at 5-10 mg/kg/day on the same day; 3) as soon as open-label caffeine is no longer deemed necessary, stop open-label caffeine and restart study drug at the next regularly scheduled time for study drug; 4) there should be no need to unblind the treatment group, since published studies have suggested that it is safe to give the suggested dose of open-label caffeine to either treatment group.³ If the attending physician thinks unblinding may be needed they should contact the clinical site principal investigators.

Pulse oximeter recordings will continue through hospital discharge, or at home through 1 week following discontinuation of study drug, for infants recruited at sites participating in home oximeter recording. The PMA at which study drug is scheduled to end is well after the clinical team judged it safe to stop routine caffeine treatment and at a PMA at which prior studies have shown that the extent of IH no longer differs from healthy infants born at term. However, **for sites continuing oximeter recordings at home**, the oximeter alarms may be activated for this final study week if deemed necessary by the clinical site principal investigators.

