7.2 PARTICIPANT DISCONTINUATION/WITHDRAWAL FROM THE STUDY

Each study participant may withdraw consent at any time during the study without penalty. In the event a participant is discontinued and thus no longer receiving the study drug, the participant will be asked to continue with follow-up assessment as described below, and not considered withdrawn from the study. If the participant refuses further follow-up, then the participant will be considered to be withdrawn. Counseling about the participant's health will be provided if the participant decides to discontinue participation in the study. Medical advice regarding what is in the best interest of the participant will be provided.

All data collected up to the time of withdrawal will be reported. The End of Study eCRF will be completed, with the reason for withdrawal specified.

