8 STUDY ASSESSMENTS AND PROCEDURES

8.1 EFFICACY ASSESSMENTS

8.1.1 OXYGEN SATURATION

Continuous recording of O₂ saturation using the study pulse oximeter is planned for all infants through hospital discharge, **and for the sub-group of infants recruited at hospitals participating in home oximetry recording, will continue through 43 weeks + 6 days PMA (i.e. one week following the last dose of study drug).** The study oximeter will be the Masimo RAD-97, set at the minimum possible averaging time of 2–4 sec and a sampling rate of 1 sec (high resolution). The oximeter will be preset in the sleep lab mode, hence with no “probe off,” “low battery,” or physiologic visual displays or alarms. The internal data storage capacity of the RAD-97 oximeter is sufficient for 28 days of continuous data collection.

Inpatient Phase: During the inpatient phase, the RAD-97 will be a 2nd oximeter, in addition to the one used for standard monitoring in the NICU. Continuous oximeter recordings will be obtained whenever in the NICU. Data will be downloaded from the monitor, and archived by the DCC, at least every 4 weeks while in the NICU and at discharge.

Please note: Some sites may discontinue oximeter recordings at hospital discharge.

Outpatient Phase: **At sites participating in the home oximetry portion of the study,** prior to discharge, the family will be trained in the use of the RAD-97, and will be asked to use the oximeter during all sleep times and quiet awake periods until 43 weeks + 6 days PMA. At home, therefore, we expect at least 8 – 12 hours of use per day, so the memory capacity of the RAD-97 should be sufficient to complete the outpatient phase.

Following discharge, the family will be contacted within the first 2 – 3 days, and then at least weekly to provide support in the use of the study monitor and to support other aspects of the study protocol. As part of their support of the use the monitor at home, study site staff will assess if the use pattern is such that the oximeter memory might be close to capacity, and determine if it is necessary to schedule an additional data download.

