8.1.5 BRIEF INFANT SLEEP QUESTIONNAIRE (BISQ)

The Brief Infant Sleep Questionnaire (BISQ) is a parent-reported questionnaire on infant/toddler sleep over the prior one week. It includes 13 items in three categories (sleep duration, night wakings, and method of falling asleep). The BISQ will be completed by phone during the weekly phone call that is scheduled between 42 weeks 0 days and 42 weeks 6 days, or in person, at study termination if this occurs prior to 42 weeks + 0 days.

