9 STATISTICAL CONSIDERATIONS

9.1 STATISTICAL HYPOTHESES

Primary Objective 1: Compare the extent of **IH** exposure, from randomization through 42 weeks + 6 days PMA (within each gestational week and overall), in infants randomized to extended caffeine treatment to infants assigned to receive placebo. *We hypothesize that caffeine will reduce the extent of IH compared to placebo, and that this caffeine effect will persist through 42 weeks PMA.*

Primary Objective 2: Compare changes in a panel of inflammation-related cytokines and chemokines, from enrollment to the target age of 38 weeks + 0 days PMA, in infants randomized to extended caffeine treatment to infants assigned to receive placebo. *We hypothesize that continuing caffeine treatment will be associated with less inflammation compared to placebo.*

Primary Objective 3: Compare changes in quantitative MRI structural, microstructural and metabolic biomarkers of acute injury, from enrollment to 43-46 weeks PMA, in infants randomized to extended caffeine treatment to infants assigned to receive placebo. *We hypothesize that continued caffeine treatment compared to placebo will be associated with 1) greater white matter microstructural organization, 2) improved neuronal metabolism, and 3) greater regional brain volume.*

Secondary Objective 1: Examine the association between salivary caffeine concentrations and **IH** outcomes at the one week post randomization and 40 weeks + 0 days PMA assessments. *We hypothesize that those with higher salivary caffeine concentrations will have less severe IH outcomes.*

Secondary Objective 2: Determine whether caffeine effects on changes in inflammatory or MRI biomarkers from baseline to follow-up are mediated by caffeine-related reduced **IH**. *We hypothesize that caffeine effects on changes in inflammatory or MRI biomarkers will be at least partially mediated by reduced IH.*

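### Schedule footnote 8 ties the end-of-study visit to the last dose, which conflicts with the sections that follow every infant to a fixed PMA, including infants who stop study drug early

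*Combined protocol and SAP*

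**What the plan says.** Footnote 8 to the Schedule of Activities (Section 1.3) says the end-of-study visit "is targeted for 43 + 6 days, or one week after the last dose of study drug, whichever comes first", with 46+6 as the latest date. At that visit, "Study staff will collect the study drug log, used bottles, unused drug, study oximeter, and frozen salivary sample". Footnote 1 to the same schedule states: "finally, the last dose of study drug is at 42 + 6".

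Other sections bear on infants who come off drug, or on when recording and the study end:

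- Section 7.2, on an infant no longer receiving study drug: "the participant will be asked to continue with follow-up assessment as described below, and not considered withdrawn from the study".
- Section 5.4 sets analysis by intention to treat, with every randomized infant kept in the assigned arm.
- Section 9.1, Primary Objective 1, compares IH "from randomization through 42 weeks + 6 days PMA (within each gestational week and overall").
- Section 8.1.1: home recording at participating sites "will continue through 43 weeks + 6 days PMA (i.e. one week following the last dose of study drug").
- Section 6.5.1: for infants at those sites, recording runs "at home through 1 week following discontinuation of study drug". The synopsis (Section 1.1) is similar.
- The synopsis (Participant Duration), Section 2.2.1, Section 6.3 and the schedule's own column place the end at 43+6. Section 7.3 places the visit between 43+0 and 46+6.
- Section 8.1.5 lets the sleep questionnaire be done in person "at study termination if this occurs prior to 42 weeks + 0 days".

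**The concern.** The last-dose alternative in footnote 8 does nothing for an infant who completes dosing. It takes effect only when drug stops early, and it then targets a visit that takes away the oximeter before the weekly IH endpoint has ended. Section 7.2 promises these infants further follow-up but sets out no off-drug schedule, so a site is likely to turn to the Schedule of Activities and its footnotes.

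The late PMA weeks are at stake. Section 9.4.2 says the primary analysis is to show how long caffeine keeps its advantage, using week-specific tests. If recording ends because drug ended, missing data in those weeks follow treatment discontinuation. That can differ by arm and can be related to IH, and the late comparisons then drift towards infants still on drug. Unrecorded oximetry cannot be recovered at analysis.

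Safety data are touched as well. Footnote 6 runs the weekly calls only through the end-of-study visit, and Section 8.3.4 lists that visit as one possible last day of participation for non-serious adverse events. This applies at any site, with or without home oximetry.

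**Working it through.** **1. The plan's own power figure.** Inputs from Section 9.2: 100 infants per group, effect 0.50 SD, overall two-sided 0.05 with family-wise correction across weeks (Holm, Section 9.4.2). At the first Holm step with k weekly tests, power = Φ(0.50 × √(100/2) − z), where z is the normal quantile at 1 − 0.05/(2k) and 0.50 × √50 = 3.536.

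- k = 7 (weeks 36 to 42): z = 2.690, power 80.1%.
- k = 6: power 81.5%.

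The stated 82% is reproduced to within 2 points, and nothing below disputes it.

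**2. Dates.** 42+6 plus 7 days is 43+6, so the two dates in footnote 8 are the same day for an infant who completes dosing. For a last dose at s+0, the footnote targets the visit for (s+1)+0.

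**3. Weekly endpoints lost.** Section 9.2 names weeks 36 to 42, which is 42 − 36 + 1 = 7 weeks. If recording ends at about (s+1)+0, weeks s+1 to 42 are lost, which is 42 − s weeks:

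- last dose 36+0: recording ends about 37+0, 6 of 7 weeks lost;
- last dose 38+0: recording ends about 39+0, 4 of 7 lost (weeks 39, 40, 41 and 42);
- last dose 40+0: recording ends about 41+0, 2 of 7 lost;
- last dose 42+6: none lost.

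**4. Who is affected.** Section 8.1.1 plans recording through discharge for all infants, and sites without home oximetry may stop at discharge whatever the drug status. The oximetry loss therefore falls mainly on discharged infants at home-oximetry sites who stop drug permanently more than a week early.

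**5. Whether the analysis rules would catch it.** Section 9.4.2 keeps an infant in the IH analysis with 10 hours of acceptable data in at least one PMA week, so an early stopper stays in the set with the later weeks missing. Section 9.4.1 triggers multiple imputation, as a sensitivity analysis, when loss to follow-up exceeds 10%. An early stopper who completes the visit is not lost to follow-up, so the trigger need not fire.

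**6. Possible bias (assumed inputs).** The documents give no early-stop rate. Suppose all stoppers are off recording before the week analysed and run g SD higher on log IH than non-stoppers. Dropping them then shrinks the placebo-minus-caffeine difference by (placebo stop rate − caffeine stop rate) × g:

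- equal rates, or g = 0: no bias;
- 15% v 5%, g = 1: 0.10 × 1 = 0.10 SD understated, one fifth of the planned 0.50;
- 5% v 15%, g = 1: −0.10 × 1 = −0.10, so 0.10 SD overstated.

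**7. Precision (assumed inputs, k = 7).** If 5, 10, 15 or 20% of 100 analysable infants per group lack a late week, n is 95, 90, 85 or 80 and power is 77.5, 74.7, 71.5 or 68.2%. If a 10% loss comes out of the 110 randomized instead, n = 99 and power is 79.6%. If stoppers are kept at n = 100 and those on caffeine retain no effect (a worst case), the average effect is 0.475, 0.45, 0.425 or 0.40 and power is 74.8, 68.9, 62.4 or 55.5%. Keeping them corrects what is estimated. It does not by itself raise power.

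**The case against.** The strongest answer is that one footnote stands against the body of the protocol. The synopsis, Sections 2.2.1, 6.3, 7.3 and 8.1.1, and the schedule's column heading all end the study by PMA. Section 7.2 points to follow-up described below it, and what comes next is Section 7.3 with its 43+0 to 46+6 window. Footnote 8 gives a target and allows completion to 46+6. This stands: a site that follows those sections keeps the data. However, no text says which passage governs, and the footnote is in the table that sites work from.

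A reader might infer that the synopsis and Section 6.5.1 repeat the early-stop rule. They need not. Section 6.5.1 goes on to discuss the scheduled end of drug, and the synopsis has just given 42+6 as the last dose. Both are ambiguous. Nor does Section 8.1.5 show that stopping drug ends the study, because early termination there fits family withdrawal equally well.

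Sections 6.3 and 6.5.1 describe interruptions for side effects or open-label caffeine as holds, with study drug restarted once open-label caffeine ends, and preliminary studies saw no recurrent apnea-related symptoms. This narrows the affected group to permanent stoppers, although no text says when a hold becomes a last dose. Families whom a site discontinues for consistent non-compliance (Section 7.1) might not record at home in any case.

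On safety, Section 8.3.4 also lists the follow-up MRI visit as a possible last day, and serious events are collected for 30 days afterwards. The shortening therefore concerns weekly calls and non-serious events, and it may not always occur.

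On missing data, Section 9.4.2 mentions multiple imputation if missing data become a problem. That sentence stands under Secondary Objective 1, sets no threshold, and is not attached to the weekly primary tests.

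**Conclusion.** The contradiction is real. As written, footnote 8 targets an early end of study only for infants who permanently stop study drug before 42+6. For them it conflicts with Sections 5.4, 7.2 and 9.1 and with the PMA-based end dates elsewhere. Where a site follows the footnote, discharged infants at home-oximetry sites lose 42 − s of the 7 weekly endpoints for a last dose at s+0, and weekly adverse-event calls may end early at any site.

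Three stronger readings are not supported:

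- That the protocol ends follow-up for every early stopper. Several sections say otherwise, so the loss depends on which text a site follows.
- That the late-week comparison is biased by 0.10 SD. That figure rests wholly on the assumed 15% v 5% stopping and 1 SD gap. The bias is zero if stopping is balanced and unrelated to IH, and its direction reverses if the rates do.
- That the 82% power is wrong. It reproduces, and the allowance from 110 to 100 infants per group may absorb some loss.

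The passages should be reconciled. The reason is that the missing data would follow treatment discontinuation and the analysis rules need not detect it, not that a bias of known size has been shown.

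**What to change.** - **Footnote 8:** remove the alternative that ties the visit to the last dose, along with its earlier-of-the-two rule. Target the visit for 43+6, no later than 46+6, for every randomized infant.
- **Sections 1.1 and 6.5.1:** match Section 8.1.1. At participating sites, home recording runs through 43+6 whether or not study drug was stopped early.
- **Section 7.2:** state that home oximetry (where applicable), weekly calls and the 42-week sleep questionnaire continue to their PMA-based dates after drug stops, unless the family withdraws from follow-up.

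End of drug and end of follow-up are then separate, and the point at which a hold becomes a last dose no longer affects follow-up. No dose, rescue or treatment-stopping rule changes. Unused drug need not wait for the visit, because the protocol already allows items to be shipped back.

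The cost is a wording amendment that uses existing procedures, plus some burden: a few families off drug keep the oximeter and the calls for longer. The amendment history (Section 10.4) itself describes home oximetry as hard for parents and a possible barrier to enrollment, so this burden is small but not nil.

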2 INTRODUCTION

2.1 STUDY RATIONALE

Caffeine treatment for apnea of prematurity and related **intermittent hypoxia (IH)** is almost universal, with treatment most commonly discontinued at 33-35 weeks PMA. However, **IH** continues to occur in infants after routine discontinuation of caffeine, and persists after hospital discharge. This **IH** is not apparent clinically and accurate detection requires continuous high resolution pulse oximetry recordings. Studies confirm that the **IH** occurring during spontaneous breathing after stopping routine caffeine is a manifestation of immature breathing control. **It is unknown if this persistent IH results in acute injury, and in particular if extending the duration of caffeine treatment attenuates or prevents this acute injury.** This study will address 3 critical questions: **1)** will extending caffeine treatment from 32-35 to 42 weeks PMA reduce extent of **IH**, **2)** is persisting **IH** associated with biochemical, structural, or functional indicators of acute injury, and **3)** does caffeine treatment continued to 42 weeks PMA attenuate this acute injury? This study has the potential to (1) identify early brain injury mediated by **IH** and mitigated by caffeine at appropriate dosing, and (2) help inform optimum strategies for later definitive neurodevelopmental assessments based on nature of the acute brain injury. This study thus has high potential to justify future neurodevelopmental outcome studies that will further improve outcomes of infants born preterm, change clinical practice, and have significant public health benefit.

2.2 BACKGROUND

Acute morbidities can contribute to adverse neurodevelopment outcomes in preterm infants born at ≤ 30 weeks gestation, but neural damage occurring after resolution of acute morbidities may be more subtle and related to cycles of inflammation and repair in the developing brain. One possible contributor to these more subtle injuries is **intermittent hypoxia (IH)**, defined as repetitive cycles of hypoxia and re-oxygenation, which occur commonly in convalescing premature infants. **Caffeine** treatment can improve both motor and cognitive neurodevelopmental outcome in premature infants, especially at **higher doses**, but mechanisms are unclear.¹⁻⁸ The Caffeine for Apnea of Prematurity (CAP) Trial in infants born preterm at <1250 g reported **1)** shorter duration of positive pressure ventilation and reduced rate of bronchopulmonary dysplasia (BPD) in infants treated with caffeine during the early postnatal weeks prior to 34-35 weeks postmenstrual age (PMA), **2)** improved motor function and reduced rates of developmental coordination disorder at 5 years, and **3)** diffusion changes by MRI consistent with improved white matter microstructural development.^{7,9,10,11} Although potential mechanisms for this caffeine effect were not studied in these reports, a recent study of very preterm infants in postnatal weeks 1-10 showed for the first time a **direct link between IH and motor, cognitive and language impairment** at 18 months corrected age (adjusted risk gradient $p<0.005$).¹² Notably, the greatest risk gradient was at postnatal ages 9-10 weeks, consistent with a contributory role of later **IH** present after stopping routine caffeine treatment. These data emphasize the potential importance of recurrent episodes of **IH**, as convalescing infants approach term-equivalent age, on later cognitive, language and motor impairments.

Studies confirm that **IH** during the early postnatal weeks of life in very preterm infants may be due to other mechanisms, including ineffective ventilation or other acute morbidities. However, **IH** in

spontaneously breathing convalescing infants is due to ventilatory immaturity with associated respiratory pauses or brief apneas, and has a characteristic pattern of brief desaturation from a **normoxic baseline** followed by reoxygenation and return to normoxia.¹³⁻¹⁸ Our study will assess **IH** only during spontaneous breathing in infants after resolution of acute morbidities or need for supplemental O₂, and approaching term-equivalent age, a time when **IH** has been shown by us and others to be the consequence of immature breathing regulation.

IH during spontaneous breathing related to ventilatory immaturity requires continuous high resolution pulse oximetry recordings for detection, and consists of brief, repetitive cycles of O₂ desaturation from a normoxic baseline, followed by return to baseline saturations. These repetitive cycles of reoxygenation following each **IH** episode are pro-inflammatory and cause oxidative stress, free radical production, and release of pro-inflammatory cytokines.^{19,20} Studies show increased levels of inflammatory biomarkers in animal models of **IH**-associated obstructive sleep apnea (**OSA**) and in human subjects with **OSA**.^{19,21-25} Although inflammatory biomarkers may be elevated in the first 2-3 postnatal weeks in very preterm infants who develop **BPD** and neurodevelopmental sequelae, it is **unknown if later IH during spontaneous breathing in convalescing preterm infants is associated with inflammation or other biochemical, structural or metabolic acute injury or adverse consequences.**²⁶⁻³¹

We have reported that clinically unrecognized **IH** events are still common after discontinuing routine caffeine treatment, typically at 34-35 weeks PMA.¹⁸ Except for 1 study, however, the potential **adverse consequences of IH have not been investigated** in human infants.^{12,18,32-34} In obstructive sleep apnea, however, even modest amounts of chronic **IH** have been associated with significant neurocognitive morbidity.^{23,24} Worrisome evidence from animal models also shows that **IH** has significant and long lasting effects on multiple physiological control mechanisms^{20-24,35-40} and neurological outcomes.⁴¹⁻⁴³ *We hypothesize that persistent IH in spontaneously breathing preterm infants after stopping routine caffeine treatment is associated with acute adverse consequences.*

The relationship between **IH**, adenosine, caffeine and brain development is complex and not fully understood. At clinically effective doses, caffeine exerts effects in the brain by blocking adenosine (Ado) A1 and A2A receptors, resulting in respiratory stimulation and increased alertness, vigilance and arousal.⁴⁴⁻⁶⁰ Ado A1 receptor activation contributes to hypoxia-induced reduction in cerebral myelination and ventriculomegaly. Caffeine treatment attenuates the effects of hypoxia, presumably through blockade of Ado A1 receptors.^{45,58,59} It is thus reasonable to hypothesize that similar mechanisms may be active in the human preterm infant. **Caffeine may thus be neuroprotective** through **two major mechanisms: 1)** reducing incidence and severity of **IH** due to its respiratory stimulatory effects, and **2)** reducing pre- and immature oligodendrocyte injury.

Brain development progresses through a highly programmed series of events.⁶¹⁻⁶⁴ Myelination in the cerebral hemispheres begins to accelerate at ~30-32 weeks and continues to term and beyond, and disturbances in these late gestation developmental processes often result in failure of normal brain growth, abnormal cortical organization, impaired myelination, and connectivity, commonly observed in surviving preterm infants.⁶⁴⁻⁷⁵ Persisting **IH** thus has even greater potential for later neurodevelopmental

disability than the **IH** associated with obstructive sleep apnea.^{23,24,76-84} Since **IH** can be attenuated with extended caffeine, **persisting IH may thus be a modifiable cause of a previously unrecognized additional risk for disabilities** associated with preterm birth.^{7,18,41,42,45,55,73,85-88}

In summary, the period from 32-35 to 42 weeks PMA is a **critical time for brain development**, and is also a time when **significant IH during spontaneous breathing is present, but the adverse effects of this IH are unknown**. As the first step in understanding acute injury from **IH**, we address a fundamental and critically important question with high potential public health benefit: **does continued caffeine treatment after receiving the last dose of routine caffeine between 32 weeks + 0 days PMA and 36 weeks and 5 days PMA reduce extent of IH and attenuate indicators of acute injury at 43-44 weeks PMA?** We will assess injury in 4 domains: biochemical (inflammation), structural (MRI), functional and metabolic (MRS). Our proposed study thus has the potential to have major impacts on clinical practice: **1) how clinicians assess and interpret IH, and 2) duration of pharmacological treatment with caffeine. This will be the first study in human infants to assess the effects of continuing caffeine treatment in attenuating acute injury indicators associated with IH.**

